### **Randomization**

According to the digital random numbers generated by SPSS.17.0 software, all participants will be assigned to experimental group (group E), placebo group (group P) and control group (group C) randomly and equally. For minimal risk bias of selection and others, a specific appointed researcher ([name]) will be in charge of the process of randomization. A sequence number will be allotted to an ensured qualified subject and a sealed envelope method is used to reduce allocation bias: the envelope is dark and opaque, sealed, content inside can't be seen even under bright light.

### **Blind method**

In this trail, the TEAS operator ([name]), statistician ([name]), data collector ([name]), trail administrator ([name]) work independently and follow the blind method. All investigators will only perform his/her assign task and there will not be direct communication between all investigators privately regarding this proposed study. The group assignments are only aware of by TEAS operator ([name]). For the test of blinding to participant, a survey about how they are think about their treatment received will be achieved to determine whether single- or double-blind of this trail is.

### **Intervention**

Surgical day, the subject will be transferred into operation room and calms down for few minutes with a supine position lying on the surgical bed. Acupoint stimulation administered at 30 min before epidural administration and 30 min after wound closed 2/10 HZ and the intensity adjust to maximal tolerance by participant until end of treatment. The acupuncture points are selected on

the basis of WHO Standard International Acupuncture Nomenclature, and zusanli (ST36, downward 3 inches to the hollow of patellar ligament lateral, Fig.2 a), sanyinjiao (SP6, 3 inches above the top of malleolus medialis, Fig.2 b), neiguan (PC6, 2 inches to the midpoint of wrist skin crease, Fig.2 c), quchi (LI11, the lateral end of the elbow crease when elbow flex 90 degree, Fig.2 d) are located specifically as figure.2 shown. After acupoint area disinfected by 75% alcohol, a medical electrode will be placed on the acupuncture points and connecting to an electro-acupuncture stimulator (SDZ-V, Suzhou medical technology Co. Ltd., Suzhou, China).

### **Experimental group**

TEAS uses unilaterally. When TEAS administered in group E, a maximal stimulus intensity need to find out by a test of each personal tolerance before anesthesia and keep the intensity through the entire surgery. Check the TEAS treatment discontinuously and guarantee all procedures normal. The operator has to observe the condition of patient because the TEAS may cause to some side effects, an emergency actions will be used when necessary.

### **Placebo group**

EAS uses unilaterally. When EAS administered in group P, a maximal stimulus intensity need to find out by a test of each personal tolerance before anesthesia and keep the intensity through the entire surgery. Check the EAS treatment discontinuously and guarantee all procedures normal. The operator has to observe the condition of patient because the EAS may cause to some side effects, an emergency actions will be used when necessary.

### **Control group**

The subject in group C will obtain a sham stimulation, which means the medical electrode adheres to the same acupuncture points as experimental group without actual electrical stimulus (or

attached to an inactive electrical stimulator). All other procedures else are same as the participant in group E except for stimulation intensity.

### **Study protocol**

All participants will fill a demographic information sheet (including age, gender, height, weight, ASA classification status, education level, income, previous anesthesia experience/complications, medical history, anxiety and depression, preoperative examination and based line functional ability). The first assessment of patient status will take place at 1 day before surgery (baseline), and repeat at 1st day, 3rd day, 7th day after surgery.

**Safety Assessment:** We will define an adverse event as an event if more than three subjects suffer a same symptom, such as local skin rash, dizziness, and low blood sugar during the treatment-evaluation period. These events will be statistically analyzed, and treatment safety is evaluated in accordance with the research protocol. If serious adverse events occur, we will report it immediately and take actions accordingly.

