### **Study subject**

The study subject is elder inpatient who will be undergoing elective total knee arthroplasty under epidural anesthesia, age from 65 to 85 years old, ASA physical status of I-III, and agree to the informed consent form. The exclusion criteria are the subject (1) refuse to participate in the study; (2) already participate in other clinical studies; (3) is not available due to severe physical status, like ASA classification of IV; (4) required emergency patient; (5) is not suitable to TEAS requirement, e.g. pace maker or metal implant; (6) has deficiency in cognition and literacy and medical history of mental disorder, deep venous thrombosis, or history of drug abuse and acupuncture. Subject should be removed if he/she: (1) switch to general anesthesia; (2) refuses to continuous TEAS administration without any excuse; (3) gets serious adverse reactions in treatment period (e.g. cardiac arrest, comatose); (4) can't accomplish the follow-up visit; (5) acupuncturist changed; (6) low compliance patient.

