### **Outcome Measures**

Primary outcome measure: The primary outcome is the Quality of Recovery-40 questionnaire (QoR-40). It was specifically designed to evaluate quality of recovery in subject after surgery with including five aspects: emotional state, physical comfort, psychological support, physical independence and pain. There are 40 items in total, each adding 1-5 points to the score. Thus, the highest possible score is 200 points; higher scores indicate better quality of recovery. The QoR-40 will be evaluated at preoperative day 1 and postoperative day 1, 3, 7, respectively.

Secondary outcome measures: a. Incidence of postoperative complications: we will assess incidence of postoperative complications when initially find by participant or accompanying family members and diagnosed through examination or scale. Any complication after surgery will be recorded and filled in the case report form. When subject send back to ward, we will require the accompanying family members to record any complaint from subject. Assessment of incidence of postoperative complications will be going on three times and occur at postoperative day 1, 3, 7, respectively. b. The length of hospital stay (LOH): The LOH = the day of patient discharge from hospital – the day of patient admit to hospital, which is calculated base on the Hospital Information System. c. Level of stress response: The Adrenocorticotropic Hormone (ACTH), Cortisol (COR) are chosen to address the level of perioperative stress response. Blood sample taken intravenously and collected at the time of 1 day before surgery (baseline) and 1st day, 3rd day after surgery, respectively. d. Level of inflammatory response: In clinic, the C Reactive Protein and Neutrophil-lymphocyte ratio are well-known to represent the level of perioperative inflammatory response [27, 28]. Blood sample taken intravenously and collected at the time of 1 day before surgery (baseline) and 1st day, 3rd day after surgery, respectively.

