### **Statistical Analysis**

1. Content of statistical analysis: a. Dropout sample: the accuracy numbers lost and dropout rate of subjects are described, and reasons for the dropout is given. b. Balance comparison: The

comparability of subjects in two groups are compared via the baseline information assessing. c. Efficacy analysis: we will treat the QoR-40 as the primary outcome to evaluate the efficacy of TEAS treatment in improving the postoperative recovery after total knee arthroplastic, a mean and deviation as the expression of primary outcome and compared between groups using one-way ANOVA (SNK method), however, before statistic performed, a test of normal distribution of data should be used to determine whether the data are suitable for analysis using the one-way ANOVA. Additional four composite outcome measures (incidence of any postoperative complication, length of hospital stay, level of stress response, level of inflammatory response) are also used as secondary outcomes to determine the efficacy of

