### **Methods of Statistical Analysis**

According to the principle of intention-to-treat (ITT), our data will contain all subjects enrolled. Efficacy and safety measures will be analyzed in accordance with protocol strictly, thus, only subjects who completed the entire trial and followed the protocol requirements should be analyzed. Quantitative and qualitative variables are described statistically with  $X \pm SD$  and count numbers, separately. Quantitative variables will be analyzed by one-way ANOVA (SNK method) in statistic, a normal data distribution needed before performance. Qualitative variables will be analyzed using either  $\chi^2$  test or Fisher' s exact test. All statistical tests are two-sided, and P value  $< 0.05$  will be considered to be statistically significant. Statistical analysis will be performed using SPSS 17.0 software for application.

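### A symptom counts as an adverse event only when more than three subjects have it, so non-serious symptoms in one to three subjects drop out of the safety analysis

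*Combined protocol and SAP*

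**What the plan says.** The Safety Assessment paragraph (protocol, Study protocol) sets the definition: "We will define an adverse event as an event if more than three subjects suffer a same symptom". It gives local skin rash, dizziness and low blood sugar as examples, and continues: "These events will be statistically analyzed, and treatment safety is evaluated in accordance with the research protocol". Serious events are handled apart, with no subject count: "If serious adverse events occur, we will report it immediately and take actions accordingly".

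Two other places bear on the safety data.

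- Methods of Statistical Analysis restricts the safety set: "Efficacy and safety measures will be analyzed in accordance with protocol strictly, thus, only subjects who completed the entire trial" and followed the protocol. The sentence just before it invokes intention-to-treat and all enrolled subjects.
- Study subject lists, among the reasons for removal, a subject who "gets serious adverse reactions in treatment period (e.g. cardiac arrest, comatose").

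Outcome Measures has a parallel route without a threshold: "Any complication after surgery will be recorded and filled in the case report form". After return to the ward, "we will require the accompanying family members to record any complaint from subject". Data collection gives safety assessment its own place in the case report form.

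**The concern.** Whether an adverse event has occurred should be decidable for one subject, when it occurs. Here it depends on how many other subjects have the same symptom, so an event in one patient cannot be classified until the others have been observed. The following sentence sends only events that pass the count to analysis.

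This matters because the plan expects side effects. The Experimental group and Placebo group sections set stimulation to each subject's maximal tolerance and ask the operator to watch for them. Non-serious reactions such as rash or dizziness are the kind that the threshold filters out.

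Absolute rates of non-serious events can only be understated. The effect on the comparison between arms has no fixed direction, because the counting unit is not stated.

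**Working it through.** **Inputs.** The threshold is more than three subjects, so at least four (Safety Assessment). There are three arms of equal size (Participants; Randomization). The documents give no symptom rates, so the rates below are assumptions.

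**Arm size.** Sample Size Calculation gives 21 per group, 26 with dropout, and 54 in total. Its formula reproduces: (1.96 + 1.282)² × (11.1² + 13.7²) / 12.6² = 20.58, rounded up to 21; 21 × 1.2 = 25.2, rounded up to 26. That calculation is for two groups, so the size of group E in a three-arm trial is unclear. I use both readings: 54 / 3 = 18 per arm, or 26 per arm and 26 × 3 = 78 in total.

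**Largest pattern in one arm that is left out.** Three cases in group E and none elsewhere, with exact (Clopper-Pearson) 95% intervals:

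- 3/18 = 16.7% (3.6% to 41.4%)
- 3/26 = 11.5% (2.4% to 30.2%)

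Under either counting rule this is zero adverse events. On a per-arm count, up to 3 × 3 = 9 subjects could share a symptom that is never counted.

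**Probability of being left out.** Let X be the number of subjects with the symptom, binomial with n subjects at risk and rate p. The symptom fails the threshold when X ≤ 3. That includes X = 0, where nothing is lost, so the last column conditions on at least one case: P(1 ≤ X ≤ 3) / P(X ≥ 1).

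| Assumed rate and where | n | P(X ≤ 3) | Left out, given at least one case |
|---|---|---|---|
| 5%, group E only | 18 / 26 | 99% / 96% | 98% / 95% |
| 10%, group E only | 18 / 26 | 90% / 74% | 88% / 72% |
| 20%, group E only | 18 / 26 | 50% / 21% | 49% / 20% |
| 10%, groups E and P, trial-wide count | 36 / 52 | 51% / 22% | 50% / 22% |
| 5%, all arms, trial-wide count | 54 / 78 | 72% / 45% | 70% / 44% |
| 10%, all arms, trial-wide count | 54 / 78 | 20% / 4% | 20% / 4% |

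Worked line (10%, group E only, n = 18): P(X = 0) = 0.9¹⁸ = 0.150 and P(X ≤ 3) = 0.902, so P(1 ≤ X ≤ 3) = 0.752 and 0.752 / 0.850 = 0.88.

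**Effect on the comparison between arms.** On a per-arm count, 3 cases in E and 0 in C become 0 against 0, which hides an imbalance; 4 in E and 3 in C become 4 against 0, which creates one. On a trial-wide count, a symptom with three or fewer cases disappears from every arm.

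**The case against.** **Other routes capture the data.** Serious events have no threshold, any postoperative complication is recorded, family members note complaints, and the case report form has a safety section. This stands as a limit: the defect lies in classification and analysis, mainly of non-serious symptoms, and not necessarily in collection. But the complication route is a secondary efficacy outcome, applies after surgery, and calls for diagnosis by examination or scale. A reaction during stimulation before the epidural is not clearly covered, and nothing says how a complication differs from an adverse event.

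**The text may be incomplete.** The list in Statistical Analysis breaks off after "are also used as secondary outcomes to determine the efficacy of", and a safety item could have followed. So the absence of a per-subject definition can be asserted only for the readable text. The explicit rule in Safety Assessment still stands.

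**The examples are not significant.** Three against none gives a two-sided Fisher p of 0.23 or 0.24 between two arms of 18 or 26. A value near 0.03 arises only by pooling groups P and C, a contrast the plan does not specify. True, but a non-significant test does not justify reporting three cases as zero.

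**The probabilities rest on assumed rates.** They do, and the highest ones require reactions confined to group E, although group P is also stimulated and group C wears electrodes. The table therefore includes the less favourable scenarios.

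**The completer restriction is a separate problem, and the intention-to-treat sentence is left out of account.** It is a distinct defect, and that sentence contradicts the restriction, so the two must be reconciled. It does not cancel the explicit restriction of safety measures, and correcting the definition alone would not bring the excluded subjects back.

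**Conclusion.** The concern holds. This is a wrong stated rule, not missing detail: applied as written, it leaves any non-serious symptom in one to three subjects out of the safety analysis. The existence of the defect does not depend on the assumed rates or on the counting unit; its size depends on both. Over the scenarios shown, assuming equal arms of 18 or 26, the chance that an observed symptom is left out runs from 4% (10% in all arms, 78 subjects, trial-wide count) to 98% (5% in group E only, 18 per arm).

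It must be corrected before safety results are analysed, because the only stated analysis of non-serious adverse events cannot give valid rates. The consequence is confined to safety reporting.

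**What to change.** 1. **Safety Assessment.** Define an adverse event as any untoward medical occurrence in any subject during the treatment-evaluation period. State the first and last day of that period. Record each event per subject with severity and relatedness, and say how adverse events and postoperative complications are told apart or cross-reported.
2. **Reporting.** Give the number and percentage of subjects with each event by arm, with exact confidence intervals, among all subjects who had any stimulation or sham session. A frequency cut-off may govern table layout only.
3. **Methods of Statistical Analysis.** Remove the restriction of safety measures to protocol-following completers, and reconcile that sentence with the intention-to-treat sentence before it.
4. **Study subject.** Add a sentence that the data of subjects removed for serious adverse reactions stay in the safety analysis.

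The cost is wording in three sections; the case report form already has a safety section. The safety table becomes longer and the reported counts somewhat less favourable. Treatment and the QoR-40 analysis do not change.

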### **Data collection**

For data collection, the case report form (CRF) is established, in which demographic information, medical history, clinical characteristics, primary and secondary outcome measures, recovery assessment, follow-up, safety assessment are arranged and covered. All investigators are asked to follow the requirement of the CRF instruction, as well as complete the form in a timely and precise way.

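### Efficacy is limited to those who followed the protocol, but adherence has no criterion, data source or named judge, and delivered stimulation is not named as recorded data

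*Combined protocol and SAP*

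**What the plan says.** - **Who is analysed.** Methods of Statistical Analysis opens with the intention-to-treat principle, then says of efficacy and safety that "only subjects who completed the entire trial and followed the protocol requirements should be analyzed". Study subject lists six reasons for removal. They include refusing to continue TEAS, failing to complete follow-up, and low compliance, which is not explained.
- **What is delivered.** Intervention has "the intensity adjust to maximal tolerance by participant until end of treatment". Under Experimental group the instruction reads: "a maximal stimulus intensity need to find out by a test of each personal tolerance before anesthesia and keep the intensity through the entire surgery". The wording for the placebo arm is parallel: "When EAS administered in group P, a maximal stimulus intensity need to find out by a test of each personal tolerance before anesthesia". Group C has electrodes at the same points; the text there reads "without actual electrical stimulus (or", and the alternative it offers is a stimulator that is not active. No output value or range is given for any arm.
- **What is recorded.** Experimental group and Placebo group ask that the treatment be checked from time to time, but not that settings, times or interruptions be written down. Data collection names demographic information, medical history and clinical characteristics, and adds that "primary and secondary outcome measures, recovery assessment, follow-up, safety assessment are arranged and covered".
- **Who knows the arm.** Blind method states: "The group assignments are only aware of by TEAS operator". The statistician, data collector and administrator are described as working independently under blinding.

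**The concern.** Membership of the efficacy set depends on adherence, and the plan leaves open how adherence is judged, from what data and by whom. The intervention is set individually, so without a record of it nobody can verify afterwards that a given patient did or did not receive it as planned. The person placed to see delivery knows the arm.

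Two things are at stake. First, exclusions after randomisation can differ between arms for reasons related to outcome, and here they could be made with knowledge of the arm. Second, without delivery data a null result for E against C could not be separated from under-delivery, and exposure in E could not be compared with exposure in P.

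**Working it through.** **1. Is adherence defined anywhere?** Study subject gives low compliance as a reason for removal, with no threshold or judge. Methods of Statistical Analysis uses following the protocol as the entry condition, again with neither. Statistical Analysis promises dropout numbers and reasons, but reasons that concern delivery could not be checked against any named record.

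**2. Is there a planned exposure to judge against?** Intervention places stimulation at 30 minutes before the epidural and 30 minutes after wound closure, with intensity adjusted until treatment ends. Experimental group and Placebo group have the intensity found before anaesthesia and kept through the whole operation. These give different pictures of duration and of whether intensity is changed or held, and must be reconciled.

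**3. Which removal reasons depend on the arm?** Only those tied to receiving current are confined to E and P, because C receives none. A switch to general anaesthesia, missed follow-up, a change of acupuncturist, refusal to continue, or poor compliance with visits can occur in any arm.

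**4. The plan's own figures.** Inputs from Sample Size Calculation: means 176.9 and 164.3 (difference 12.6), SDs 11.1 and 13.7, Z values 1.96 and 1.282.

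n = (1.96 + 1.282)² × (11.1² + 13.7²) / 12.6² = 10.51 × 310.90 / 158.76 = 20.58, so 21 per group, as stated. Adding 20% gives 21 × 1.2 = 25.2, so 26, as stated. The total of 54 equals 2 × 27 (21 / 0.8 = 26.25, so 27), which is a two-group total although three groups are randomised. That is a separate matter; 26 per group is used below.

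**5. Illustration of what one-sided exclusion can do.** All inputs except 26 and 12.6 are assumptions. Suppose k of n = 26 are dropped from E and none from C, with no treatment effect involved, and those k score D = 10 points lower.

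- If they score D below the patients retained, the arm mean rises by kD/n.
- If they score D below the full-arm mean, it rises by kD/(n − k).

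| k | kD/n | kD/(n − k) | share of 12.6 |
|---|---|---|---|
| 1 | 0.38 | 0.40 | 3% |
| 2 | 0.77 | 0.83 | 6–7% |
| 4 | 1.54 | 1.82 | 12–14% |
| 5 | 1.92 | 2.38 | 15–19% |

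The shift is proportional to D, so D = 5 halves every entry.

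**6. Upper bound.** A simulation removed the k lowest scorers from one arm. It used 26 per arm, SD √(310.90/2) = 12.47, no true difference, a two-sided two-group t-test and 20,000 runs. Type I error was 5.1% at k = 0, 6.6% at k = 1, 9.3% at k = 2, 13.1% at k = 3 and 23.0% at k = 5. The induced differences were about 1.0, 1.8, 2.6 and 4.0 points for k = 1, 2, 3 and 5. Five of 26 is 19%, close to the planned 20% dropout. This is a worst case: nothing in the documents indicates that patients would be selected by outcome.

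**The case against.** Several stronger readings are tempting, and the documents do not support them.

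- *The operator decides who is analysed.* A reader might infer this because the operator observes delivery and knows the arm. No section assigns the compliance decision to anyone. What can be said is that the decision-maker is unspecified.
- *Delivery is not recorded at all.* Data collection lists broad categories and the form itself is not in the documents. Clinical characteristics or safety assessment could contain delivery fields, and all investigators, a term that appears to include the operator, are told to complete the form. What can be said is that delivery is not named.
- *Only the stimulated arms can lose patients.* This holds for exclusions tied to current, not for the other removal reasons.
- *Poor tolerance is non-compliance.* Intensity is set to tolerance, so a patient on a low setting is following the protocol. Arm-dependent loss needs more than that, for instance a patient refusing further stimulation because of the current.
- *Duration follows the length of surgery.* Intervention can be read as two fixed periods, so duration is unresolved rather than known to vary.
- *The bias is 12–14% of the planned difference.* The arithmetic is right but its inputs are assumed. It also measures exclusion after randomisation, not the lack of a log: a logged rule that dropped the same four patients would give the same shift.

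The operator and data collector are also kept apart, which makes deliberate selection by outcome unlikely. It does not remove bias when the reason for exclusion is itself related to recovery.

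What remains against the plan is the written restriction to an undefined adherent set. The intention-to-treat sentence does not protect against it, because the sentence that follows sets it aside.

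**Conclusion.** The point holds in a limited form and should be acted on. The plan restricts efficacy to an adherent set whose criterion, data source and decision-maker are all unstated. Delivered intensity and minutes are not among the data named for collection although intensity is individual in E and P, and the only role placed to observe delivery is unblinded. An unblinded decision about who is analysed is therefore possible; it is not shown to be planned.

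The documents give no size for any bias. The shifts and error rates above rest on assumed one-sided exclusions and show only that a handful of patients per arm would matter at this sample size. Without the restriction to adherent patients, the missing log and definition would be close to missing detail; the restriction is what makes them matter.

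**What to change.** 1. In Methods of Statistical Analysis, make the analysis of all randomised subjects in their assigned groups primary for efficacy, and the adherent set supportive only. This is the step that deals with the bias. It needs QoR-40 scores to go on being collected, where the patient agrees, after any deviation, so Study subject should say that low compliance affects membership of the adherent set and not outcome collection.
2. Under Data collection, add a one-page stimulation log: output setting, start and stop times, interruptions and their reason. Keep it from the data collector and statistician until database lock.
3. Before the first patient, define adherence by a rule that applies equally to all three arms, for example session minutes with electrodes attached. Output intensity should not enter the rule, because it would reveal group C. Name a person other than the operator to apply it, using only the arm-neutral entries and without sight of outcomes.
4. Report delivered intensity and minutes by arm.
5. Reconcile the timing and intensity wording in Intervention with that in Experimental group and Placebo group, so that there is a planned exposure to judge adherence against.

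The cost is one extra form page, completed by the operator who is already present, and a few sentences of protocol and analysis text.
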